## **Statement of Compliance**

This study will be conducted in accordance with the Code of Federal Regulations on the Protection of Human Subjects (45 CFR Part 46), any other applicable US government research regulations, and institutional research policies and procedures. The Principal Investigator will assure that no deviation from, or changes to the protocol will take place without prior agreement from the sponsor and documented approval from the Institutional Review Board (IRB), except where necessary to eliminate an immediate hazard(s) to the trial participants. All personnel involved in the conduct of this study have completed Human Subjects Protection Training.

## List of Abbreviations

AE	Adverse Event/Adverse Experience
CFR	Code of Federal Regulations
CRF	Case Report Form
CSOC	Clinical Study Oversight Committee
DCC	Data Coordinating Center
DSD	Delirium Superimposed on Dementia
DHHS	Department of Health and Human Services
DSMB	Data and Safety Monitoring Board
FFR	Federal Financial Report
FWA	Federalwide Assurance
GCP	Good Clinical Practice
HIPAA	Health Insurance Portability and Accountability Act
ICF	Informed Consent Form
IRB	Institutional Review Board
ISM	Independent Safety Monitor
MOP	Manual of Procedures
N	Number (typically refers to participants)
NIH	National Institutes of Health
OHRP	Office for Human Research Protections
OHSR	Office of Human Subjects Research
PI	Principal Investigator
PLWD	Persons Living with Dementia
QA	Quality Assurance
QC	Quality Control
SAE	Serious Adverse Event/Serious Adverse Experience
SOP	Standard Operating Procedure
US	United States

CONFIDENTIAL

This material is the property of the NYU Langone Health. Do not disclose or use except as authorized in writing by the study sponsor

## Protocol Summary

Title	Development and Piloting of a Family-Centered, mHealth-Enhanced Intervention to Promote Caregiving Mastery in Detection, Prevention, and Management of Delirium Superimposed on Dementia
Short Title	A Pilot Study of the Aliviado DSD Caregiving Mastery Program
Brief Summary	Delirium superimposed on dementia (DSD) is an acute and serious condition that is common in persons living with dementia (PLWD). Involvement of family caregivers may aid prevention, early detection, and management of DSD. The purpose of the proposed study is two-fold. First, we will develop a family-centered, mHealth-enhanced DSD caregiving mastery program ("Aliviado DSD Caregiving Mastery Program") through a 5-week co-design workshop with 8 family caregivers (Aim 1). We will adapt/refine the existing clinician-centered DSD contents and an mHealth app from the evidence-based "Aliviado Dementia Care" program for use by family caregivers to support their day-to-day implementation of DSD detection, prevention, and management tasks in the community. Second, we will pilot test the full Aliviado DSD Caregiving Mastery Program with 30 family caregivers of PLWD at high risk for delirium, assessing feasibility, acceptability, app usability, and preliminary program impact (Aim 2).
Phase	Phase I (NIH Stage I)
Objectives	

To adapt the existing Aliviado app for use by family caregivers

Assess feasibility, acceptability, app usability, and preliminary impact of the Aliviado DSD Caregiving Mastery Program.

Methodology	

Co-design workshop

A single-arm, pre-post study

Endpoint	Primary endpoints: feasibility, acceptability, and app usability Secondary endpoints: caregivers' delirium knowledge, caregiving mastery, strain, depression, and burden
Study Duration	12 months
Participant Duration	10 months
Duration of behavioral intervention	6 weeks
Population	Adult family caregivers of community dwelling PLWD. "Adults" are individuals who are 18 years of age and older. "Family caregivers" are relatives or friends who provide unpaid care to PLWD.
Study Sites	NYU and University of Pittsburgh
Number of participants	Aim 1: 8 family caregivers Aim 2: 30 primary caregivers plus 0 to 30 optional secondary caregivers Optional: Enrolled primary caregivers can choose to invite additional relatives or friends to participate in the Aim 2 pilot study as "secondary caregivers".
Description of Study Intervention/Procedure	Intervention: Aliviado DSD Caregiving Mastery Program, a family caregiver intervention consisting of mHealth-app based educational videos and articles; caregiver-administered assessment tools and care plans; and motivational push notification or text message reminders and encouragements.
Reference Therapy	None
Key Procedures	None

CONFIDENTIAL

This material is the property of the NYU School of Medicine and Langone Health. Do not disclose or use except as authorized in writing by the study sponsor

Statistical Analysis	
Aim 1: Descriptive statistics to describe sample characteristics
 
Aim 2: Descriptive statistics will be calculated to summarize caregiver characteristics, feasibility, acceptability, and app usability outcomes. Paired t-tests will be performed to compare (1) changes in caregiver delirium knowledge and caregiving mastery from baseline to Week 2 (immediately post training), and (2) changes in delirium knowledge, caregiving mastery, strain, depression, and burden from baseline to posttest (Week 6).

----------------------	---

[figure not shown]
CONFIDENTIAL

This material is the property of the NYU Langone Health. Do not disclose or use except as authorized in writing by the study sponsor

Behavioral Intervention Template Version: 18 July 2022

## Schematic of Study Design

Figure 1. Aim 1 Codesign Workshop

[figure not shown]

CONFIDENTIAL

This material is the property of the NYU Langone Health. Do not disclose or use except as authorized in writing by the study sponsor

Behavioral Intervention Template Version: 18 July 2022

Figure 2. Aim 2 Feasibility Trial

CONFIDENTIAL

This material is the property of the NYU Langone Health. Do not disclose or use except as authorized in writing by the study sponsor

## 2 Introduction, Background Information and Scientific Rationale

### 2.1 Background Information and Relevant Literature

Delirium Superimposed on Dementia (DSD) refers to occurrence of delirium (i.e., a serious, acute, fluctuating disturbance in attention and cognition) in persons living with dementia (PLWD). DSD is highly prevalent in PLWD, affecting 22% to 89% of PLWD in the community and hospital settings. Compared to dementia alone, those with DSD have accelerated cognitive and functional declines and higher rates of rehospitalization, institutionalization, and death. Moreover, DSD causes substantial distress and burden to both PLWD and family caregivers—defined here as relatives and friends that provide unpaid care.

Research shows that it is feasible for family members to perform delirium assessment to aid early detection and assist with delirium prevention and management tasks to address modifiable risk factors. The purpose of this project is to develop and pilot test a family-centered, mHealth-enhanced intervention program to improve caregivers' knowledge, skills, and mastery in DSD detection, prevention, and management in the community. The proposed intervention, the "Aliviado DSD Caregiving Mastery" program, will adapt existing DSD components in the clinician-focused, evidence-based "Aliviado Dementia Care" program for use by family caregivers. "Aliviado" means "relief" in Spanish/Portuguese. The original Aliviado Dementia Care program is an agency-wide quality improvement program to optimize home-based, clinician-delivered symptom management for PLWD and their families. The existing Aliviado DSD contents include a DSD education video for aides, a clinician-initiated acute delirium care plan, a clinician-administered delirium assessment, and an acute delirium caregiver education article, all accessible via a clinician-facing Aliviado mHealth app. While these contents are a solid template for the proposed intervention, with the exception of the caregiver education article (written for both professional caregivers and family caregivers), the remaining DSD contents require adaptation for direct use by families. Moreover, to promote caregivers' self-efficacy/mastery, we include additional strategies informed by Pearlin's Stress Process Model, Bandura's Social Cognitive Theory (e.g., social support and goal setting), and Nudge Theory. The proposed study aligns with Stage I of the NIH Stage Model.

#### 2.1.1 Theoretical Framework/Mechanism

The DSD Caregiving Mastery Program is informed by the Stress Process Model, Social Cognitive Theory (including the Threefold Stepwise Implementation Model), and Nudge Theory. In the Stress Process Model (Figure 3): The "primary stressors" are the patient's cognitive status, problematic behaviors, and dependencies of activities of daily living, and the caregiver's felt sense of overload and relational deprivation. The "secondary stressors" are role strains and intrapsychic strains including *global mastery* and *situational competence*. This intervention program is designed to address a specific type of situational competence, DSD caregiving mastery. The "mediators" are coping and social support.

DSD accelerates cognitive and functional declines and can worsen behavioral issues, yet different from dementia, delirium is often preventable and reversible. Thus, the prevention and early detection tasks can help reduce the additional situational caregiving stress resulting from DSD-induced cognitive and functional declines and worse behavior symptoms at the "primary stressors" level. The inclusion of a **caregiver strain assessment and referral to community supportive services as part of this intervention helps to address the "secondary role strains"** in the Stress Process Model. The tailored care plan with specific DSD management strategies addresses the "mediator" of coping, while the ability to include a secondary caregiver helps to activate the "mediator" of social support. To address "secondary intrapsychic strains" in the Stress Process Model, we adopt Social Cognitive Theory-informed strategies to promote mastery and competence. For instance, training videos with successful case scenarios provide *observational learning/vicarious experience*, meanwhile increase caregivers' DSD knowledge/skills to improve *behavioral capabilities* and *competence*. Practicing delirium assessment using case vignettes as part of the caregiver training provides caregivers with *mastery experiences* in DSD detection, which contributes to increased *self-efficacy* and *mastery*. The tailored care plan facilitates *goal setting*. The additional support to help caregivers with lower self-efficacy to set incremental goals

CONFIDENTIAL

This material is the property of the NYU Langone Health. Do not disclose or use except as authorized in writing by the study sponsor

follows the guidance in Bandura's Threefold Stepwise Implementation Model. Lastly, we use Nudge Theory-informed mobile push notifications or text messages to provide text-based *verbal persuasion*, and nudge caregivers to perform the target prevention, detection, and symptom management behaviors. (See 6.1 and Table 2 for more detail.)

Figure 3. Screenshot of Pearline's Stress Process Model

[figure not shown]

Figure 1. A conceptual model of Alzheimer's caregivers' stress. The stress process is made up of four domains: the background and context of stress; the stressors; the mediators of stress; and the outcomes or manifestations of stress.

According to the Stress Process Model, improved mastery and competence may contribute to improved caregiver outcomes such as improved depression and anxiety. Therefore, we decide to also measure caregiver depressive symptoms to find out whether improved DSD caregiving mastery and competence are related to improved depressive symptoms in caregiver participants as a group (on average).

This study does not diagnose depression nor screen for positive depression cases.

## 2.2 Rationale

Research shows that it is feasible for family members to perform delirium assessment to aid early detection and assist with delirium prevention and management tasks to address modifiable risk factors. However, most delirium/DSD interventions involving families have been developed for hospital/institutional settings and have not considered different education/training needs of multiple caregivers within the same family. Moreover, although mHealth apps for dementia caregivers have burgeoned, no DSD interventions have leveraged mHealth-based behavioral economics nudges, or motivational messages and prompts, to reinforce family caregivers' implementation of DSD prevention, detection, and management tasks in the community. Thus, there is a considerable gap between what is feasible and the available interventions to support family caregivers to provide DSD care in the community.

The duration of the caregiver education/training period in the proposed intervention, the Aliviado DSD Caregiving Mastery Program, is set at 2 weeks to allow caregivers plenty of time to complete the self-paced training. The duration of the implementation period is set at 4 weeks to assess whether caregivers

CONFIDENTIAL

This material is the property of the NYU Langone Health. Do not disclose or use except as authorized in writing by the study sponsor

can perform weekly screening in the mHealth app for at least several times without major issues. Findings from this pilot feasibility trial will reveal feasibility and acceptability of the proposed frequency of delirium assessment and intervention duration, which will inform further refinement of the Aliviado DSD Caregiving Mastery Program in preparation for a future efficacy trial.

Given that this is a pilot study to assess feasibility, acceptability, and preliminary impact of the intervention on family caregivers, all caregiver participants will receive the intervention (a single-group, pre-post design). There are no control groups nor PLWD subjects in this pilot study. After feasibility and acceptability of the intervention are established in family caregivers, we will then add control groups and enroll PLWD-caregiver dyads in future efficacy and effectiveness trials of the Aliviado DSD Caregiving Mastery Program.

## **2.3 Potential Risks & Benefits**

### **2.3.1 Known Potential Risks**

This is a minimal risk study. The intervention itself is inherently not risky as it is a family-centered, psychoeducational training program on implementation of evidence-based best practices through an mHealth app to improve family caregivers' mastery in performing DSD detection, prevention, and symptom management tasks. The greatest potential risks to family caregiver subjects are (1) a breach of confidentiality and (2) psychological distress.

Though possible, we anticipate that a breach of confidentiality is unlikely to happen because personal identifiers will only be collected and stored in the password-protected REDCap electronic consent and HIPAA authorization form, in which only authorized study team members will have access to, whereas all the other study data will be deidentified and stored in a password-protected NYU Box folder, in which access will only be granted to appropriate study team members. NYU Box is the NYU WSQ Campus approved storage of [high-risk data](#).

When learning something new such as a new mHealth app, some caregivers can become frustrated or experience psychological distress. However, we believe psychological distress is unlikely to happen, because we will have tested our mHealth app to ensure user-friendliness. We will also proactively offer additional technical support/training sessions on how to use the study app via Aliviado Support Center ([contact]) to caregivers who report a lower level of comfort with technology at enrollment (caregivers are free to decline this offer/additional support). If caregiver subjects experience psychological distress or become frustrated with the technology, they can contact Aliviado Support Center ([contact]) for assistance. If participants do not feel comfortable answering depressive symptom questions or any questions in any of the study questionnaires, they have the option to select "prefer not to answer" as their response. Subjects may also experience psychological distress when answering questions about their depressive symptoms and will also have the option to select "prefer not to answer".

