Aim 2 feasibility trial: n=30 to 60 (30 primary caregivers + 0-30 optional secondary caregivers); single site. The enrollment goal is 30 primary caregiver participants. The 30 enrolled primary caregivers are allowed to invite additional family members or friends to participate in the study and enroll as secondary caregivers. However, the enrollment of secondary caregivers is optional, and thus, we anticipate 0 to 30 secondary caregivers will be enrolled. To ensure the study is adequately powered, we need 26 evaluable primary caregiver participants who complete the study. We will recruit additional primary caregivers if more than 4 primary caregivers drop out of the study, or the number of primary caregiver participants who complete the study has not reached 26. Single site: All participants will be screened, enrolled, and consented at the NYU Site; all data will be collected and stored in the password-protected NYU REDCap or NYU Box as appropriate. Data will be deidentified before uploading to NYU Box. Subjects will be recruited from a list of potentially eligible caregivers identified in the data pull performed by the DataCore. The screening and consenting of all caregiver subjects will be completed by the PI or an NYU research assistant trained by the PI following the “Remote e-Consenting” process using “REDCap” as described in the [“Use of Electronic Informed Consent”](#) guidance document. We will create the REDCap version of the IRB-approved consent form following the [NYU Health Science Library video series on eConsent](#).

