**Week 6 Final Visit (n=30 primary caregivers + up to 30 secondary caregivers)**

- Collect data on caregiver participants’ delirium knowledge, DSD caregiving mastery, caregiver strain, depressive symptoms, burden, program satisfaction, and app usability in an online REDCap survey questionnaire.

Also see Attachment C for schedule of events.

\*We will stick with CES-D to collect data on depressive symptoms. We were considering replacing it with PHQ-9 because PHQ-9 is a shorter questionnaire. We decided to still use CES-D because it does not ask about suicidal ideation. All de-identified baseline caregiver depressive symptom raw scores will only be analyzed as a group and presented as mean/sd/range (or median/interquartile range/range if not normally distributed).

If a high level of symptoms are found from CES-D, such as depressive symptoms, we will offer to refer subjects to support services that may help with these, such as the NYU Alzheimer’s Caregiving Program. This information will remain confidential and will not be shared with others.

CONFIDENTIAL

This material is the property of the NYU Langone Health. Do not disclose or use except as authorized in writing by the study sponsor

If a high level of caregiving strain is found, we will offer to refer subjects to support services that may help, such as the NYU Alzheimer's Caregiving Program, however this information will remain confidential and will not be shared with others. If the depressive symptom score has increased for 15 or more points from the baseline/enrollment visit for a subject, our medical monitor, [name], (a board-certified nurse practitioner) will call the subjects to better understand their change in depressive symptoms; determine whether it is related to their study participation; and will refer them to mental health or emergency services as needed.

*Rationale for change score:* We will calculate the mean and range of the change score from baseline to posttest as a group (=all caregivers' scores lumped together).

If the upper limit of the range of the group change score is below 15, then it means that no one in the group has a substantial increase in their depression score and we will not reach out to any participants about their depressive symptoms.

If the upper limit of the range of the group change score is 15 or above (out of the 60-point CES-D scale), we will look up the participants who have a change score  $\geq 15$  and notify the medical monitor.

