#### **10.4.3 Analysis of the Secondary Endpoint(s)**

Paired t-tests will be performed to compare changes in delirium knowledge and caregiving mastery from baseline to 2 weeks (immediately post training), and changes in delirium knowledge, caregiving mastery, caregiver strain, depression, and burden from baseline to posttest (Week 6); effect sizes (Cohen's d) will be reported for all outcomes. To maintain the familywise error rate, we will use Bonferroni-adjusted alpha to determine significance.

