### **10.5 Sample Size**

Aim 1 co-design workshop: We aim for 5-8 participants per session based on recommendations from Smaradottir et al. and our consultation with a Design Thinking expert from the Emory Roybal Center Design Studio. Accordingly, the target sample size is 8 caregivers (plus 8 on the waitlist).

Aim 2 feasibility trial: Because improvement in delirium knowledge should occur before improvement of caregiver mastery, our power calculation is based on delirium knowledge. Home health aides exposed to the current Aliviado videos demonstrated medium-to-large knowledge gains (Cohen's  $d = .64$ ). We will have 80% power to detect an effect of this magnitude in 26 caregivers, using a Bonferroni adjusted significance level of  $\alpha = .025$ . The expected gains will likely be larger, as previous research with a similar delirium intervention using telephone-based education modules found even greater improvement at 2 weeks (Cohen's  $d = .86$ ) and 2 months ( $d = .87$ ) post-intervention, and our projected sample of 26 will yield >99% power to detect similar effects. To allow for a 12% dropout rate and remain adequately powered, we aim to recruit 30 caregivers.

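### The 15-point CES-D check reads a caregiver with declined items as showing no rise, and the 26 needed for power counts completers, not usable knowledge pairs

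*Combined protocol and SAP*

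**What the plan says.** **Declining items.** Section 2.3.1 covers caregivers who are uneasy about the depression items or "any questions in any of the study questionnaires, they have the option to select" a prefer-not-to-answer response. The same section expects that the depression items may cause distress.

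**The CES-D check.** Under the Week 6 Final Visit in Section 7.1.1, a rise of 15 or more points leads to a call from the medical monitor. Such caregivers are found through the group's range. The rule for a low maximum reads "upper limit of the range of the group change score is below 15, then it means that no one in the group" shows a marked rise, and nobody is then approached about depressive symptoms. Individual scores are looked up only if that maximum is 15 or more. The section describes the CES-D as a 60-point scale, and Table 4 in 14.1.1 gives it 20 items.

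**The tests and the sample size.** Section 10.4.3: "Paired t-tests will be performed to compare changes in delirium knowledge and caregiving mastery from baseline to 2 weeks", and on five outcomes from baseline to Week 6. Section 10.5 bases power on delirium knowledge (19 items in Table 4), with d = .64 and a Bonferroni-adjusted alpha of .025: "We will have 80% power to detect an effect of this magnitude in 26 caregivers". It adds: "To allow for a 12% dropout rate and remain adequately powered, we aim to recruit 30 caregivers". Section 5.6 says "we need 26 evaluable primary caregiver participants who complete the study". Sections 5.6 and 5.7.2 keep recruiting until 26 have completed.

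**What is absent.** Sections 10.3 to 10.4.6 do not say how a scale with declined items is scored, and 10.1 says no separate SAP will be written. Evaluable is not defined.

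**The concern.** A declined item is an allowed answer, so a scale total with a gap is a foreseeable result. Two parts of the plan depend on such totals.

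The first is the CES-D check. It moves from the largest computed change to a statement about every caregiver. That step is valid only if every caregiver has a correctly scored change. A caregiver with no computable change does not enter the range, and one whose declined items were added as zero enters it with the wrong value. Section 2.3.1 itself anticipates discomfort with these items, so the gap could fall among the caregivers the check is meant to find.

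The second is the power statement. It needs 26 usable pairs, while the replacement rule counts completers. A caregiver who attends every visit but has no usable knowledge pair counts toward 26 and is not replaced.

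**Working it through.** **1. The plan's own figure.** Inputs from 10.5: d = 0.64, n = 26, alpha = .025. Sidedness is not stated; two-sided reproduces the claim. For a paired t-test with df = n − 1 and noncentrality d√n = 0.64 × √26 = 3.26, power is 0.804, and 26 is the smallest n that reaches 80%. Dropout: 26 / 0.88 = 29.5, rounded up to 30. Both figures reproduce.

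**2. Margin.** The same formula with other numbers of usable pairs:

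| Pairs | 30 | 26 | 25 | 24 | 22 | 20 |
|---|---|---|---|---|---|---|
| Power | 0.866 | 0.804 | 0.785 | 0.764 | 0.719 | 0.666 |

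**3. CES-D, total set to missing.** There is no change score, so the caregiver contributes nothing to the range. A maximum below 15 says nothing about that person. This needs no assumption about how often items are declined.

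**4. CES-D, declined items summed as zero.** 60 points over 20 items gives at most 60 / 20 = 3 points per item, assuming equal item ranges. With m items declined at Week 6 and a true rise R, the recorded rise can be as low as R − 3m. It can fall below 15 when R ≤ 14 + 3m:
- one item: true rises of 15 to 17 can be masked
- two items: up to 20
- three items: up to 23

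These are limits; an item whose true answer was below 3 hides less. With m items declined at baseline, the recorded rise can be as high as R + 3m, so one item can turn a true rise of 12 into 15 (12 + 3 = 15), which is a false alert.

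**5. Knowledge pairs lost if any declined item voids the total.** The decline rate q per item is not in the documents. Assuming independent refusal, the share lost over 2 × 19 = 38 item answers is 1 − (1 − q)^38:

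| Assumed q | Share lost | Pairs left of 26 | Power |
|---|---|---|---|
| 0.1% | 4% | 25.0 | 0.785 (25 pairs) |
| 0.5% | 17% | 21.5 | 0.693 to 0.719 (21 to 22) |
| 1% | 32% | 17.7 | 0.575 to 0.607 (17 to 18) |

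Independence spreads refusals over the most people. With refusals clustered within persons (beta-binomial, assumed intraclass correlation 0.1 to 0.3), the loss is about 4 to 7% at q = 0.5% and 7 to 14% at q = 1%. Power is then about 76 to 79% and 72 to 76%.

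**The case against.** The study team has several safeguards. Visits are 1:1 (7.3.2 to 7.3.4) and the investigators complete the questionnaires from caregiver report (14.1.1), so a refusal is seen when it happens. Weekly review and validation checks cover all forms (Sections 9 and 12). Section 7.1.1 also offers referral for high CES-D symptoms, and 8.4.1 and 8.7 add distress reports and medical-monitor assessment. A declined item is an explicit response, so a competent analyst is unlikely to score it as zero unnoticed. The trial is a single-arm pilot whose primary endpoints are descriptive.

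Much of this stands, and it limits the weight of the point. But completeness checks do not say how a permitted refusal is scored, the referral offer also depends on the CES-D result, and 8.4.1 describes its monitoring as passive. None of these alters the inference written in 7.1.1.

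A reader might infer four stronger things that the documents do not support:
- *That the count of 26 is itself made on scale totals.* Sections 5.6 and 5.7.2 count completers; totals enter only through the power calculation.
- *That a caregiver scored low can never reach 15.* With one zero-scored item, a true rise of 18 or more still does.
- *That zero-scoring at Week 6 flatters every outcome.* It would for strain, depression and burden, if more is declined at Week 6 than at baseline. For knowledge and mastery it looks like worsening.
- *That 17 to 32% of pairs will be lost.* That rests wholly on assumed independent refusal rates. All 30 enrolled caregivers may also complete, which gives a start above 26.

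**Conclusion.** The point holds on two counts.

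- **CES-D check.** Sections 2.3.1 and 7.1.1 do not fit together. Followed as written, the check can report that nobody has risen when a caregiver's change is unknown or under-recorded. For an uncomputable change this holds whatever the decline rate. For zero-scoring, the masking is bounded at 3 points per item and can also run the other way; the documents do not say that zero-scoring will be used.
- **Power.** The 80% figure has no margin at 26 pairs, and the replacement rule would not notice a shortfall in pairs. One lost pair costs about 2 percentage points (0.804 to 0.785). Larger losses depend on a decline rate that the documents do not give.

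The lack of a scoring rule for the t-tests in general is missing detail that an analyst could fill sensibly. It is still better fixed beforehand, because in an unblinded single-arm study the choice would otherwise be made with the results in view. The primary feasibility, acceptability and usability endpoints do not turn on this point. Nothing here judges the 15-point threshold.

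**What to change.** 1. **Sections 2.3.1 and 7.1.1:** reconcile them so that the check reports how many caregivers have no computable CES-D change and does not read them as having no rise. Whether and how anyone is contacted stays with the study's clinical roles.
2. **Section 10.4.1:** state that a declined item on the symptom scales (strain, depression, burden) is missing, not zero. Name in advance the rule for scoring an incomplete scale, including knowledge and mastery, and report the number of incomplete totals by scale and visit. The completeness cut-off is the sponsor's choice. For the knowledge test, counting a declined item as not correct is also defensible if stated beforehand.
3. **Section 5.6, with 5.7.2 to match:** define evaluable as a completer with a usable baseline and Week 2 knowledge pair, and recruit to 26 of those. Section 10.5 does not name the time point behind the power figure. Week 2 is assumed here because that visit directly follows training; if Week 6 is meant, say so.

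The cost is a few sentences and possibly one or two extra caregivers. If proration is chosen, it assumes that declined items resemble answered ones, so add a sensitivity table restricted to complete totals.
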